In addition to Unanticipated Problems Involving Risks to Subjects or Others, the following adverse events will be monitored: deaths, suicide attempts, study dropout, psychiatric hospitalizations, and clinical deterioration, defined as emergent suicidal ideation or suicidal plan, development of serious substance abuse, or emergence of a new psychiatric or medical diagnosis or behavior posing significant risk to the subjects of others.

The following grading system will be used to assess the seriousness of any adverse events:

0 No adverse event or within normal limits

Mild adverse event

Moderate adverse event

Severe adverse event resulting in hospitalization or a persistent or significant disability/incapacity

Life-threatening or disabling adverse event

Fatal adverse event The Ph.D. level project coordinator will be trained in what events to look for and to report any such events to [name]. If the event is graded 2-4, [name], a licensed

clinical psychologist, will interview the participant and take the appropriate action. The UCLA IRB and NIH will be notified within 24 hours of any serious adverse events (SAEs), in the 3-5 range. All SAEs will be reported to the DSMB within 2 days of their occurrence. Within a week of any SAEs, the DSMB together with [name] will determine whether the adverse event affects the Risk/Benefit ratio of the study and whether modifications to the protocol (at Risks to Subjects) or consent form (at Risks and Inconveniences) are required. Furthermore, the DSMB shall have the discretion and responsibility to recommend that the study be terminated.

[name] will conduct a review of all non-serious adverse events at least quarterly. They will evaluate the types, frequency, and severity of the adverse events and determine if modifications to the protocol or consent form are required. A summary of the non-serious adverse events will be reported to the IRB and DSMB periodically or, at minimum, when yearly re-approval of the IRB protocol is sought. The summary will include number of Participants enrolled, treatment retention and reasons for drop-out, and a description of graded adverse events to date. Dr or [name] or the IRB has the authority to stop or modify the study.

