Data Management, Analysis and Quality Assurance All data will be specifically obtained for research purposes during individual test sessions. Sources of material obtained from participants will include amygdala reactivity, skin conductance response (SCR), and subjective fear ratings in both the R61 and R33 phases. In the R33 phase the investigators will also assess spontaneous recovery with the Behavioral Approach Test (BAT) and Anxiety and Related Disorders Interview Schedule (ADIS). The identifying information that will be collected from study participants includes all information required to create a GUID: sex, first name, last name, middle name, date of birth, and city/municipality of birth. The investigators will also collect email addresses.

A member of the research team with current CITI and HIPAA certification will assign a code number to each data file. The key pairing each code number with each participant's name and other identifying information will be stored separately from the data files themselves, in a locked filing cabinet to which only declared research personnel have access. All of the interviews and study procedures will be conducted in private, locked room where only the experimenter and participant are present in order to protect each participant's privacy. The data collected will be used only for this study. Upon completion of the study, all data files will be stripped of personal identifiers and/or the key to the code destroyed. The investigators agree to follow the OHRPP Data Security in Research guidance and procedures.

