Treating Phobia With Multivoxel Neuro-reinforcement

NCT03655262

Document Date: August 5, 2022

1. H1: We will use a freesurfer segmented amygdala ROI to isolate amygdala activity. Amygdala response measured via BOLD signal to phobic stimuli will be baseline corrected by the amygdala activation corresponding to non-feared animal. Then, these extracted BOLD signals will be subjected to a repeated-measures ANOVA with 2 within-subject factors of time (Pre- and Post-treatment) and Condition (target and control) followed by twosided paired-sample t-tests.
2. H2: We will determine skin conductance responses during a time window beginning 1 second and ending 5 seconds after stimulus presentation. The amplitude of the response will be determined by subtracting the mean baseline activity during 2 seconds preceding the onset of the image from the maximum value in this time window. Responses smaller than 0.02 microsiemens (μ S) will be recorded as 0 following previous procedures (Schiller et al., 2010; Schiller et al., 2013; Taschereau-Dumouchel et al., 2018). Responses will be square root transformed to correct for skewness of the distribution of the skin conductance response (Boucsein et al., 2012; Koizumi et al., 2016).
 1. A hierarchical mixed effects model will be carried out with trials nested in subjects. The model will include 3 fixed effects (Time, Condition, and Time * Condition), and the coefficients of Time and Conditions will be allowed to have random components to correct for potential clustering of errors within subject (Raudenbush & Bryk, 2002).
 2. Simple effects analyses will be carried out using two-sided paired sample *t*- test, and by splitting the data by Condition.
3. H3: Fear ratings for each stimulus category (as described in 4.) will be averaged.
 1. A hierarchical mixed effect model with 3 fixed effects (Time, Condition, Time * Condition) will be carried out.
 2. Simple effects will be tested using two-sided paired sample *t*-test.

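### Worsening of the treated phobia is not among the monitored adverse events, and no individual criterion links fear ratings or SCR to safety review, so unreported worsening may be missed.

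*Protocol*

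**What the plan says.** **Monitored events (Protocol, Reporting Adverse Events).** Besides Unanticipated Problems, "the following adverse events will be monitored: deaths, suicide attempts, study dropout, psychiatric hospitalizations, and clinical deterioration". Deterioration is then spelled out: "clinical deterioration, defined as emergent suicidal ideation or suicidal plan, development of serious substance abuse, or emergence of a new psychiatric or medical diagnosis". A last limb of the same definition brings in conduct as well: "or behavior posing significant risk to the subjects of others".

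**Grading and review (same section).** The scale runs from no event, through mild and moderate, to fatal. Its scope is wide: "The following grading system will be used to assess the seriousness of any adverse events". The protocol also provides that a named role "will conduct a review of all non-serious adverse events at least quarterly". The periodic summary to the IRB and DSMB includes "treatment retention and reasons for drop-out, and a description of graded adverse events to date".

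**Data collected (Protocol, Data Management, Analysis and Quality Assurance).** The measures are "amygdala reactivity, skin conductance response (SCR), and subjective fear ratings in both the R61 and R33 phases". The behavioral approach test and the diagnostic interview are added as later assessments in the R33 phase only, to look at spontaneous recovery.

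**Analysis (SAP items 2 and 3).** For H3, "Fear ratings for each stimulus category (as described in 4.) will be averaged". Ratings and SCR then enter mixed models with Time, Condition and their interaction, followed by two-sided paired t-tests.

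**The concern.** The intervention is new and is meant to alter the fear response itself, outside the participant's awareness. A fear response that moves the wrong way is the harm most specific to it. The deterioration definition would suit almost any psychiatric study and contains nothing aimed at this possibility.

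At stake is how complete the safety account is. The study could report no clinical deterioration while some participants finish with a stronger fear than they brought. A favorable group mean would not show this, because a minority who worsen are averaged with a majority who improve. The data needed to see it would already be on file.

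**Working it through.** The central check is textual. The documents give no expected rate of worsening and no figure to reproduce.

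**Step 1: does the definition reach a worse phobia?** It has four limbs.
- Suicidal ideation or plan: no.
- Serious substance abuse: no.
- A new psychiatric or medical diagnosis: no. The protocol's R61 enrollment paragraph requires DSM-5 specific phobia at entry, so a more severe form of that phobia is not new. A different anxiety disorder would qualify.
- Behavior posing significant risk: only if the fear leads to such behavior.

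**Step 2: do the other monitored events reach it?** Death, suicide attempt and psychiatric hospitalization would apply only in extreme cases. Dropout catches those who leave, not those who stay. Unanticipated Problems and the grading scale could capture it, but only after someone has recognized the change as an adverse event. The project coordinator is to be trained on which events to watch for, and this one is not on the list.

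**Step 3: do the outcome data feed safety review?** The H3 averaging over stimuli gives each participant a mean rating per category and time, so individual change could be derived. The SAP then estimates group effects only. The H2 model allows a random component for Time, so variation between people is modeled, but no participant's change is listed or compared with a criterion. Neither document routes ratings or SCR to adverse-event review.

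**Step 4: can a group test look favorable while some worsen?** This is an illustration on assumed values. Only n = 30 comes from the protocol. Individual change has SD 1; improvers have mean −0.8 and worseners +1.0; negative means less fear. With k worseners, the expected mean change is [(30 − k)(−0.8) + k(1.0)]/30. For k = 3 this is (−21.6 + 3.0)/30 = −0.62. The last column is the share of 40,000 simulated trials with a significant improvement on a two-sided 5% paired t-test.

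| Worseners of 30 | Expected mean change | Significant improvement |
|---|---|---|
| 1 | −0.74 | 97% |
| 2 | −0.68 | 92% |
| 3 | −0.62 | 85% |
| 5 | −0.50 | 61% |

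**Step 5: how well would an individual flag work?** Take the same model with k = 3 and flag any change above c. Expected flags are 27 × P(Z > c + 0.8) among improvers and 3 × P(Z > c − 1.0) among worseners.

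| Threshold c | Improvers flagged (of 27) | Worseners flagged (of 3) |
|---|---|---|
| 0 | 27 × 0.212 = 5.7 | 3 × 0.841 = 2.5 |
| +1 SD | 27 × 0.036 = 1.0 | 3 × 0.500 = 1.5 |
| +1.96 SD | 27 × 0.003 = 0.1 | 3 × 0.169 = 0.5 |

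A low threshold flags more improvers than worseners, and a high one misses most worseners. A flag can prompt review but cannot serve as a count of harm.

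**The case against.** A reader might infer that a participant made more fearful is never counted as harmed, and that the DSMB would weigh risk and benefit with no sight of this harm. The documents do not support either reading. Deterioration is one of five listed categories, and Unanticipated Problems are monitored as well. Grading covers any adverse event, non-serious events are reviewed at least quarterly, and the DSMB summary carries dropout reasons and graded events. Someone who reports stronger fear can be graded mild or moderate, and nothing bars that from reaching the DSMB. Acute distress is also handled: the protocol's risk section names it, places clinicians on site, ends procedures for acutely distressed participants and refers to a written distress protocol. The SAP tests are two-sided, so a mean rise in fear is detectable.

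All of this stands, and it narrows the point to worsening that is not reported. It does not remove the point. The distress provisions deal with reactions during procedures, not a lasting increase in fear. The grading scale needs a recognized event to grade. A two-sided test of the mean does not find a minority who worsen.

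Two further objections also stand. That a mean can improve while some worsen is true of any trial, so the 85% shows what is possible and does not estimate harm here. And a laboratory rise in SCR to images is not clearly clinical harm, so recording every rise as an adverse event would go too far.

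**Conclusion.** The point holds in a limited form. The definition of clinical deterioration leaves out worsening of the treated phobia, and no individual criterion connects the fear measures to safety review. The participant at risk of being missed becomes more fearful, does not report it, completes the study and has no other listed event. For that person, systematic identification and reporting to the DSMB are not assured; the remaining routes are partial.

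How many such participants there might be cannot be derived from the documents. The range from 97% (1 worsener) to 61% (5 worseners) rests entirely on assumed effects and normally distributed change with unit SD. It shows only that a favorable group result is compatible with individual worsening. The textual conclusion does not depend on those assumptions. This is a cheap improvement to safety ascertainment and does not undermine the efficacy analysis.

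**What to change.** In the protocol's Reporting Adverse Events section, add worsening of the treated phobia to the monitored events, with a measure and criterion that the investigators fix before analysis.

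In the SAP, add a listing of each participant's post-minus-pre change in mean fear rating for the target and control categories, with SCR change as supporting information. The control category gives a reference for ordinary variation. Give the listing and the number of flagged participants to the DSMB, and include both in the results report.

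Send flagged participants to the existing clinical review, which decides whether the change is graded as an adverse event. Flags should not be counted as adverse events automatically.

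The cost is one addition to the definition and one listing from data already collected, with no new visit or measure. The review will also spend some effort on flags that are measurement noise, and some true worsening will still be missed; the threshold sets the balance between the two.

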Treating Phobia With Multivoxel Neuro-reinforcement

NCT03655262

Document Date: August 5, 2022

1. H1: We will use a freesurfer segmented amygdala ROI to isolate amygdala activity. Amygdala response measured via BOLD signal to phobic stimuli will be baseline corrected by the amygdala activation corresponding to non-feared animal. Then, these extracted BOLD signals will be subjected to a repeated-measures ANOVA with 2 within-subject factors of time (Pre- and Post-treatment) and Condition (target and control) followed by twosided paired-sample t-tests.
2. H2: We will determine skin conductance responses during a time window beginning 1 second and ending 5 seconds after stimulus presentation. The amplitude of the response will be determined by subtracting the mean baseline activity during 2 seconds preceding the onset of the image from the maximum value in this time window. Responses smaller than 0.02 microsiemens (μ S) will be recorded as 0 following previous procedures (Schiller et al., 2010; Schiller et al., 2013; Taschereau-Dumouchel et al., 2018). Responses will be square root transformed to correct for skewness of the distribution of the skin conductance response (Boucsein et al., 2012; Koizumi et al., 2016).
 1. A hierarchical mixed effects model will be carried out with trials nested in subjects. The model will include 3 fixed effects (Time, Condition, and Time * Condition), and the coefficients of Time and Conditions will be allowed to have random components to correct for potential clustering of errors within subject (Raudenbush & Bryk, 2002).
 2. Simple effects analyses will be carried out using two-sided paired sample *t*- test, and by splitting the data by Condition.
3. H3: Fear ratings for each stimulus category (as described in 4.) will be averaged.
 1. A hierarchical mixed effect model with 3 fixed effects (Time, Condition, Time * Condition) will be carried out.
 2. Simple effects will be tested using two-sided paired sample *t*-test.

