Treating Phobia With Multivoxel Neuro-reinforcement

March 23rd, 2022
NCT03655262

Treating Phobia With Multivoxel Neuro-reinforcement

Protocol and Additional Information

The objective of this study is to use the novel approach of neuro-reinforcement based on decoded fMRI information to reduce fear responses to fearful stimuli (e.g., spiders, heights) in individuals with phobias, directly and unconsciously in the brain, without repeatedly exposing participants to their feared stimuli.

Specific Aims

(1) confirm that our method engages the neurobiological target (amygdala reactivity to images of a feared object) in a population of individuals with specific phobia; and (2) to determine dosage-response optimization.

The investigators aim to enroll a total of 30 patients. The investigators seek female and male participants in equal proportions. The age range of the subjects will be between 18 and 65. The investigators will work to achieve an ethnic and racial distribution that is consistent with the very diverse community found in the Los Angeles area and the UCLA campus: Hispanic/Latino 56.4%, African American 7.7%; Asian/Filipino/Pacific Islander 15.8%; White (non-Hispanic) 17.5% (California Health Interview Survey).

Potential research participants' eligibility will be confirmed at the beginning of the first session, but eligibility criteria will also be listed in recruitment materials. A research assistant or other personnel possessing current CITI and HIPAA certification will conduct an eligibility screening interview in a private room. Following onset of the study, subjects who are unable to attend to or respond to stimuli as required by the experimental protocol will be excluded.

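### Does SAP item 1 leave open which H1 result decides whether the amygdala target was engaged?

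*SAP*

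**What the plan says.** The first item under Specific Aims in the Protocol is to "confirm that our method engages the neurobiological target (amygdala reactivity to images of a feared object"). SAP item 1 (H1) is the only SAP item that analyses amygdala response. The response to phobic stimuli "will be baseline corrected by the amygdala activation corresponding to non-feared animal", and the corrected signal enters a "repeated-measures ANOVA with 2 within-subject factors of time (Pre- and Post-treatment) and Condition (target and control"), "followed by twosided paired-sample t-tests".

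Items 2 and 3 are laid out a little differently. For skin conductance (H2): "The model will include 3 fixed effects (Time, Condition, and Time * Condition"). For fear ratings (H3): "A hierarchical mixed effect model with 3 fixed effects (Time, Condition, Time * Condition) will be carried out". Both items call their paired t-tests simple effects, and H2 runs them separately by Condition.

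Neither document states an alpha, a success criterion for Aim 1, or a rule linking the t-tests to the ANOVA. The SAP does not tie H1 to Aim 1 by name. The link is inferred because both concern amygdala response to feared images.

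**The concern.** The H1 ANOVA gives three F tests (Time, Condition, and their interaction), and an unstated number of t-tests follow. Only the interaction uses the control condition to separate a treatment effect from a general decline between the two sessions. Subtracting the response to a non-feared animal removes decline common to all images. It does not remove habituation specific to phobic images. A fall in the target condition alone, or a Time main effect, could therefore appear with no treatment effect.

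H1 names only its two factors, whereas H2 and H3 write out the interaction, so the item closest to Aim 1 looks the least specified. If the target pre/post t-test were significant and the interaction were not, the SAP has no sentence saying whether engagement was confirmed. That choice could then be made after seeing the data.

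**Working it through.** The plan states no figure to reproduce, so the check asks two things: how far the candidate tests can diverge, and which of them the plan, read normally, uses.

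**Inputs.** n = 30 is the enrolment aim in the Protocol. Two-sided 0.05 is assumed. Let D_T and D_C be each person's post-minus-pre change in the target and control conditions, with equal SD and correlation ρ, varied from 0 to 0.75. With no treatment effect, both conditions fall by the same amount d, in SD of the change score, varied from 0 to 0.5. The documents give neither d nor ρ.

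**Tests.** In a two-by-two within-subject design:
- the interaction F is the square of the paired t on D_T − D_C;
- the Time F is the square of the one-sample t on D_T + D_C, with standardised effect d × √(2/(1+ρ));
- the target pre/post t-test has noncentrality d × √30 on 29 df, with critical value 2.045.

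At d = 0.3 the target noncentrality is 0.3 × 5.477 = 1.643, which gives a rejection rate of 0.355. The shared fall cancels in D_T − D_C, so the interaction has noncentrality 0 and rejects at 0.05 for every d and ρ.

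| Shared fall d | Target t-test significant | Interaction significant | Target fall significant, interaction not (simulated, over ρ) |
|---|---|---|---|
| 0 | 5% | 5% | about 2% |
| 0.1 | 8% | 5% | 6–7% |
| 0.2 | 19% | 5% | 16–17% |
| 0.3 | 36% | 5% | 33–34% |
| 0.4 | 56% | 5% | 53–54% |
| 0.5 | 75% | 5% | 72–73% |

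The Time main effect is significant 5% of the time at d = 0, 40–61% at 0.3 and 81–96% at 0.5.

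With no habituation, taking either the interaction or the target t-test as success gives 8–10% in either direction. In the favourable direction it gives 4–5%, against 2.5% for the interaction alone.

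**Number analysed.** The Protocol lets participants be excluded after the study starts if they cannot attend or respond to stimuli, so 30 is an upper figure. With 20 analysed (assumed), the last column is about 23% at d = 0.3 and 54% at d = 0.5.

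**What the plan as written does.**
1. A repeated-measures ANOVA with two crossed within-subject factors contains Time × Condition by default. A mixed model has its terms listed. That H2 and H3 spell out the interaction and H1 does not is a difference of notation.
2. H1 places the t-tests after the ANOVA, which is the usual description of follow-up tests.
3. The same SAP labels the matching t-tests: "Simple effects analyses will be carried out using two-sided paired sample" t-tests, split by Condition, under H2, with the same label under H3. By analogy, the H1 pairs are pre versus post within each condition.
4. If the t-tests are read only after a significant interaction, the disagreement column cannot produce a claim. Over the same grid at n = 30, a significant target fall together with a significant interaction occurred in at most about 3.6% of simulated trials with no treatment effect.

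**The case for a change.** The strongest case for a change is that an aim worded as confirmation should not leave its deciding test to inference. An order of tests is not a gatekeeping rule. H2 and H3 list the interaction without making it decisive. Two or three sentences would settle the matter at no analytic cost.

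There is also an incentive to fall back on the t-test. For a true target-only fall of 0.5 SD, the interaction has effect size 0.5/√(2(1−ρ)). Its power is 47% at ρ = 0, 75% at 0.5 and 96% at 0.75, against 75% for the target t-test. Below ρ = 0.5 the t-test is the more powerful of the two.

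Much of this stands. The omission is real: no sentence in either document fills it, and the figures are correct under their assumptions. What does not stand is the step from an unwritten rule to an unsound analysis. The needed test is already in the plan, and the ordinary reading of item 1 leads to it. The large percentages need three things together: habituation specific to phobic images at a size no document supports, t-tests that include the target pre/post pair, and a team that claims engagement despite a null interaction. Insisting that the t-tests be called descriptive is also a preference, since interpreting them only after a significant interaction is equally valid. Ranking H2 and H3 as secondary would add a hierarchy the documents do not contain: the Protocol's section on data management lists amygdala reactivity, skin conductance and fear ratings together, unranked.

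**Conclusion.** The gap is one of detail, and no change to the plan is needed. Writing down the rule would record what a competent analyst would do with item 1 anyway: judge H1 on Time × Condition and use the paired t-tests to describe it. It would correct no stated rule and substitute no better method. On that reading the false-positive rate is 5%, whatever the shared habituation or the correlation between conditions.

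The 33–73% disagreement figures illustrate what would follow from relying on the target t-test against a null interaction, at an assumed habituation of 0.3–0.5 SD with all 30 analysed. They do not describe how the plan behaves. The conclusion rests on the inferred link between H1 and Aim 1, on an assumed two-sided 0.05, and on reading the H1 t-tests as the H2 and H3 ones are labelled. If a report claimed engagement from the target t-test alone, a reader could see this, because the interaction comes from the same planned ANOVA.

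### The H2 skin-conductance model gives no subject-level random component to Time × Condition, so its standard error is too small if participants differ in that contrast

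*SAP*

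**What the plan says.** SAP item 2 (H2), sub-item 1, sets up a trial-level analysis: "A hierarchical mixed effects model will be carried out with trials nested in subjects". The fixed part is listed in full: "The model will include 3 fixed effects (Time, Condition, and Time * Condition". The random part follows in the same sentence and covers two of those three coefficients: "the coefficients of Time and Conditions will be allowed to have random components to correct for potential clustering of errors within subject". The SAP gives no random component for the interaction, no robust standard error and no degrees-of-freedom method.

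The design of the two factors is stated under SAP item 1 (H1), which uses a "repeated-measures ANOVA with 2 within-subject factors of time (Pre- and Post-treatment) and Condition (target and control". Both factors are therefore within subject. H2 sub-item 2 adds two-sided paired t-tests with the data split by Condition. The sample size comes from the Protocol, Specific Aims: "The investigators aim to enroll a total of 30 patients".

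**The concern.** In a pre/post by target/control design within subjects, the treatment effect is isolated by the difference between the two pre-to-post changes, which is the Time × Condition coefficient. The SAP does not label it the key H2 test; that is inferred from the design. No other term in the model compares change between target and control.

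A random component for a coefficient lets its standard error reflect how much participants differ in it. The SAP gives this protection to the two main effects and withholds it from the interaction. Its stated reason for including random components, within-subject clustering, is then not met for the coefficient that matters most. H1 tests the same contrast against subject-level variation, because its repeated-measures ANOVA works on one value per subject and cell. The SAP gives no reason for treating H2 differently.

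At stake is whether a positive H2 interaction can be taken at face value, and whether its interval has the stated coverage.

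**Working it through.** The SAP gives no sample-size, power or variance figure for H2, so there is nothing to reproduce. The check derives the standard error under the stated model and compares it with the true one.

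**Inputs**
- N = 30 subjects (Protocol, Specific Aims).
- A 2 × 2 within-subject design with trials nested in subjects (SAP items 1 and 2).
- Assumed: K = 5, 10 or 20 trials per cell; τ = 0 to 0.75, where τ is the between-subject SD of the difference-in-differences in units of the residual SD (σ = 1); balanced data; Gaussian errors; a two-sided 5% level. A random intercept is also assumed, because trials are nested in subjects; it does not affect the contrast.

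**True variance.** Each subject's difference-in-differences of cell means has variance τ² + 4σ²/K. The subject's intercept, Time and Condition deviations cancel out of it. The mean over subjects has variance (τ² + 4σ²/K)/N.

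**Variance under the stated model.** With no random interaction, the model uses 4s²/(KN). Here s² pools the trial residual, with 4N(K − 1) df, and the subject × Time × Condition variation, with N − 1 df. Its expectation, with σ = 1, is 1 + (N − 1)(Kτ²/4) / [4N(K − 1) + N − 1].

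**Ratio of true to model standard error**

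R = √{ (1 + Kτ²/4) / (1 + (N − 1)(Kτ²/4) / [4N(K − 1) + N − 1]) }

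Worked case, K = 10 and τ = 0.5:
- Kτ²/4 = 10 × 0.25/4 = 0.625.
- Denominator: 1 + 29 × 0.625/(1,080 + 29) = 1.016.
- R = √(1.625/1.016) = 1.26.
- True SE = √[(0.25 + 0.4)/30] = 0.147. Model SE = 0.147/1.26 = 0.116 (0.1164 before rounding R).
- Approximate rejection rate under a zero mean contrast: 2Φ(−1.96/1.264) = 12.1%.

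**Simulated type I error of the stated model** (40,000 data sets per setting)

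| τ | K = 5 | K = 10 | K = 20 | R over K = 5–20 |
|---|---|---|---|---|
| 0 | 5.1% | 4.8% | 5.0% | 1.00 |
| 0.1 | 5.1% | 5.2% | 5.5% | 1.01–1.02 |
| 0.25 | 6.1% | 6.7% | 8.5% | 1.04–1.14 |
| 0.5 | 8.2% | 12.1% | 18.8% | 1.14–1.49 |
| 0.75 | 12.5% | 19.9% | 30.6% | 1.28–1.92 |

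Repeat runs agreed to within about half a percentage point, and N = 15 gave nearly the same values. A t-test on the subject-level contrasts held 4.7–5.1% throughout.

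**Check with fitted mixed models.** REML fits with random intercept, Time and Condition (N = 30, K = 10, 1,900 per setting) rejected in 4.4% at τ = 0, 6.8% at τ = 0.25 and 13.0% at τ = 0.5. In a smaller separate set of 60 fits at τ = 0.5, the mean model SE was 0.117 against the true 0.147.

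**The case against.** The strongest reply is that the size rests on assumptions. Only N comes from the documents. At τ of 0.1 or less there is nothing worth fixing, and the double-digit error rates need τ of 0.5 or more, for which the documents offer no support. This stands, and is why the whole range is shown.

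A second point is about where τ comes from. If treatment does nothing for anyone, variation in treatment response cannot create τ. Type I inflation then needs participant-specific drift that differs between target and control. Ordinary differences in skin-conductance level, habituation and stimulus reactivity are absorbed by the intercept and the listed random terms. A simulation with assumed values for these, multiplicative noise, the 0.02 µS floor and the square root, and no differential drift, gave 5.5, 5.2 and 5.7% at K = 5, 10 and 20 (4,000 each). This too stands. It does not exclude differential drift, and the interval is still too narrow when treatment response varies between people. It also shows that the table, built on Gaussian data, is illustrative.

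The SAP is brief, and its wording may be shorthand for a full random structure. But it lists all three fixed effects and then names two for random components, so an analyst following it would leave the third out.

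The paired t-tests in sub-item 2, if run on subject means, use subject-level error. Split by Condition, they test change within each condition and not the difference in change. H1, which carries the amygdala aim, is unaffected. Both points limit the damage without repairing the H2 interaction test.

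Finally, four correlated random terms mean 4 × 5/2 = 10 covariance parameters from 30 subjects, so a singular fit is possible. That calls for a stated fallback.

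**Conclusion.** The point holds, conditionally as stated: with more than one trial per cell and τ > 0, the H2 Time × Condition standard error is too small, and the shortfall grows with τ and with the number of trials. At τ = 0 it is correct. Over the assumed ranges the true standard error is 1.00 to 1.92 times the one the model reports, and type I error runs from about 5% to about 31%.

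Confidence in the mechanism is high; the size for this trial cannot be fixed from the documents. The SAP gives no reason to assume that every participant has the same contrast, so the analysis should not depend on it. This should be fixed before H2 is interpreted.

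**What to change.** In H2 sub-item 1, specify by-subject random components for the intercept, Time, Condition and Time × Condition, with Satterthwaite or Kenward-Roger degrees of freedom. State the fallback in advance: if the model does not converge, average trials to one value per subject, Time and Condition, and test the subject-level difference-in-differences with a paired t-test (29 df if all 30 are analysed). Treat a singular fit the same way.

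The cost is SAP wording and one model term, with no new data. The interval widens by the factor R in the table, apart from the change in degrees of freedom. For example, a statistic of 2.5 under the stated model (p = 0.012, normal reference) becomes 2.5/R on 29 df:
- τ = 0: p = 0.018, from the degrees of freedom alone;
- τ = 0.25: p = 0.02–0.04;
- τ = 0.5: p = 0.04–0.10;
- τ = 0.75: p = 0.06–0.20.

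H3 is a separate matter: its random part is not specified at all. A subject-level contrast test on the averaged ratings would settle it.
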